### **Design:**

- We will evaluate the combination of tremelimumab and durvalumab (with ablativ e therapies) in cohorts A1 (HCC; Barcelona clinic liver cancer staging system (BCLC) stage C; N=10), A2 (HCC; BCLC stages B/C; N=30) and B (BTC; N=30). The patients in cohort A1 and first 10 patients in cohort B will receive tremelimumab and durvalumab only (i.e. no interventional radiologic procedures).

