#### 3.4.2.4 Hepatic function abnormalities (hepatotoxicity)

Hepatic function abnormality is defined as any increase in ALT or AST to greater than  $3 \times$  ULN and concurrent increase in total bilirubin to be greater than  $2 \times$  ULN. Concurrent findings are those that derive from a single blood draw or from separate blood draws taken within 8 days of each other. Follow-up investigations and inquiries will be initiated promptly by the investigational site to determine whether the findings are reproducible and/or whether there is objective evidence that clearly supports causation by a disease (e.g., cholelithiasis and bile duct obstruction with distended gallbladder) or an agent other than the IP. Guidelines for management of patients with hepatic function abnormality are provided in [Appendix F](#).

Due to the fact that in HCC patients elevated transaminase and/or bilirubin levels are common and fluctuant as a result of underlying liver disease (e.g. viral hepatitis), the toxicity criteria outlined in [Appendix F](#) will be interpreted with the following caveats:

- 1) For patients with HCC with normal liver transaminases and/or bilirubin at baseline, the criteria apply as outlined in [Appendix F](#). (i.e. if a grade 2 event occurs treatment will be held until resolution to grade 1)
- 2) For patients with HCC who have elevated liver transaminases and/or bilirubin at baseline (grade 1 or 2 i.e. still allowing for study entry), subsequent occurrences of grade 2 elevations will not result in holding of therapy.
- 3) Grade 3 events will be treated as per [Appendix F](#) irrespective of baseline levels.

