As each of these 7 treatment arms of 10 patients will be considered a small pilot, each will have same statistical objective, and each of these arms will be evaluated for efficacy as follows. For both HCC and BTC there is no standard second-line therapy in the advanced setting. Based on historical data of investigational agents for both these diseases and stage (i.e. post-sorafenib HCC and post-gem/cis BTC) the 6-month PFS would be not greater than 10-15%[\[42, 43\]](#). In each treatment arm of 10 patients in cohorts A1, A2 and B, the trial will have 82% power to rule out 15% as the proportion stable at 6 month in favor of 50% being stable at 6 months, with each evaluation assuming that a one-sided 0.10 significance level exact binomial test would be performed. If there are 3 patients in 10 who are able to have stable disease at a 6 month evaluation, then the lower one-sided 90% confidence bound for 3/10 is 11.6% (the two sided 80% confidence interval extends from 11.6% to 55.2%). Similarly, with 4 in 10 with stable disease at 6 months, the lower one-sided 90% confidence bound for 4/10 is 18.8% (the two sided

80% confidence interval extends from 18.8% to 64.6%). Thus, in Cohorts A1, A2 or B, 3 or 4 patients out of 10 attaining stable disease at 6 months in any of the 7 treatment arms would tentatively rule out 10-15% as the fraction who would do so, with 90% one sided confidence. The results from the ablation treatment arms of cohort A2 (using TACE, RFA, or cryoablation) may also have their results combined in an exploratory fashion to report their overall efficacy. Similarly, the results from the ablation treatment arms of cohort B (using RFA or cryoablation) may also have their results combined in an exploratory fashion to report their overall efficacy.

Should positive findings be identified in any of the treatment arm of cohorts A1, A2 or cohort B, then after this pilot phase has been concluded, subsequent, more definitive evaluation may be conducted in the appropriate sub-cohorts using larger numbers of patients, as defined by amendments (or separate protocols if warranted) used to describe the expansion cohorts.

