It is expected that up to 2 patients per month may be able to enroll onto this trial. Cohort A1 will require 10 evaluable patients, Cohort A2 may require up to 30 evaluable patients and cohort B may require up to 30 evaluable patients. The accrual ceiling for the protocol will be set at 90 patients to allow for a small number of inevaluable patients to be enrolled. Thus, it is expected that 24-36 months may be needed to accrue all patients onto this trial.

To address safety and feasibility of combining tremelimumab and durvalumab in (Cohorts A1 and A2) patients with advanced HCC (either alone or with cryoablation, TACE or RFA) and (Cohort B) in patients with advanced biliary tract carcinoma (BTC) (either alone or with cryoablation or RFA), adverse events will be tabulated by grade per CTCAE 4 and analyzed and reported descriptively.

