
Hepatitis (elevated LFTs) Infliximab should not be used for management of immune-related hepatitis.
	
Any Grade
 
Grade 1 (AST or ALT >ULN and <math>\leq 3.0 \times</math>ULN if baseline normal, 1.5-3.0<math>\times</math>baseline if baseline
	
General Guidance
 
 
• No dose modifications.
 
• If it worsens, then treat as Grade 2.
 
	
For Any Grade
 
 
- Monitor and evaluate liver function test: AST, ALT, ALP, and TB.
 
- Evaluate for alternative etiologies (e.g., viral hepatitis, disease progression, concomitant medications).
 
- Continue LFT monitoring per protocol.
 

---	--	--	---

PLEASE SEE shaded area immediately below this section to find guidance for management of “Hepatitis (elevated LFTs)” in HCC patients

abnormal; and/or TB >ULN and <math>\leq 1.5 \times</math>ULN if baseline normal, >1.0-1.5<math>\times</math>baseline if baseline abnormal)
	
abnormal; and/or TB >ULN and <math>\leq 1.5 \times</math>ULN if baseline normal, >1.0-1.5<math>\times</math>baseline if baseline abnormal)
	
abnormal; and/or TB >ULN and <math>\leq 1.5 \times</math>ULN if baseline normal, >1.0-1.5<math>\times</math>baseline if baseline abnormal)

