
Grade 3 (AST or ALT >5.0<math>\times</math>ULN and <math>\leq 20 \times</math>ULN if baseline normal, >5-20<math>\times</math>baseline if baseline abnormal; and/or TB >3.0<math>\times</math>ULN and <math>\leq 10.0 \times</math>ULN if baseline normal, >3.0-10.0<math>\times</math>
	
For elevations in transaminases <math>\leq 8 \times</math>ULN, or elevations in TB <math>\leq 5 \times</math>ULN:
 
 
Hold study drug/study regimen dose until resolution to Grade <math>\leq 1</math>
 
Resume study drug/study regimen if elevations downgrade to Grade <math>\leq 1</math> within 14 days and after completion of steroid taper.
 
Permanently discontinue study drug/study regimen if the elevations do not downgrade to Grade <math>\leq 1</math> within 14 days.
 
	
For Grade 3 or 4:
 
 
Promptly initiate empiric IV methylprednisolone at 1 to 2 mg/kg/day or equivalent.
 
If still no improvement within 2 to 3 days despite 1 to 2 mg/kg/day methylprednisolone IV or equivalent, promptly start treatment with immunosuppressive therapy (i.e., mycophenolate mofetil 0.5 – 1 g every 12 hours then taper in consultation with hepatology consult). Discuss with study physician if mycophenolate is not available. Infliximab should NOT be used.
 
Request Hepatology consult, and perform abdominal workup and imaging as appropriate.
 
Once the patient is improving, gradually taper steroids over <math>\geq 28</math> days and consider prophylactic antibiotics, antifungals, and anti-PJP
 

	
baseline if baseline abnormal)
 
Grade 4 (AST or ALT >20×ULN if baseline normal, >20×baseline if baseline abnormal; and/or TB >10×ULN if baseline normal, >10.0×baseline if baseline abnormal)
	
 
• For elevations in transaminases >8×ULN or elevations in bilirubin >5×ULN, permanently discontinue study drug/study regimen.
 
• Permanently discontinue study drug/study regimen for any case meeting Hy’s law criteria (AST and/or ALT >3×ULN + bilirubin >2×ULN without initial findings of cholestasis [i.e., elevated alkaline P04] and in the absence of any alternative cause).
 
	
treatment (refer to current NCCN guidelines for treatment of cancer-related infections).

--	---	--	---

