
Hepatitis (elevated LFTs) Infliximab should not be used for management of immune-related hepatitis.
 
THIS shaded area is guidance only for management of “Hepatitis (elevated LFTs)” in HCC patients
	
Any Elevations of AST, ALT, or TB as Described Below
	
General Guidance
	
For Any Elevations Described:
 
 
– Monitor and evaluate liver function test: AST, ALT, ALP, and TB.
 
– Evaluate for alternative etiologies (e.g., viral hepatitis, disease progression, concomitant medications, worsening of liver cirrhosis [e.g., portal vein thrombosis]).
 
– For HBV+ patients: evaluate quantitative HBV viral load, quantitative HBsAg, or HBeAg
 
– For HCV+ patients: evaluate quantitative HCV viral load
 
– Consider consulting hepatologist/Infectious Disease specialist regarding change/implementation in/of antiviral medications for any patient with an elevated HBV viral load >2000 IU/ml
 
– Consider consulting hepatologist/Infectious Disease specialist regarding change/implementation in/of antiviral HCV medications if
 

--	--	--------------------------------	---

See instructions at bottom of shaded area if transaminase rise is not isolated but (at any time) occurs in setting of either increasing bilirubin or signs of DILI/liver decompensation
	
Isolated AST or ALT >ULN and <math>\leq 5.0 \times \text{ULN}</math>, whether normal or elevated at baseline
	
 
No dose modifications.
 
If ALT/AST elevations represents significant worsening based on investigator assessment, then treat as described for elevations in the row below.
 
For all transaminase elevations, see instructions at bottom of shaded area if transaminase rise is not isolated but (at any time) occurs in setting of either increasing bilirubin or signs of DILI/liver decompensation
 
	
HCV viral load increased by <math>\geq 2</math>-fold For HCV+ with HBcAB+: Evaluate for both HBV and HCV as above

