	
If transaminase rise is not isolated but (at any time) occurs in setting of either increasing total/direct bilirubin (≥1.5×ULN, if normal at baseline; or 2×baseline, if >ULN at baseline) or signs of DILI/liver decompensation (e.g., fever, elevated INR):
 
Manage dosing for each level of transaminase rise as instructed for the next highest level of transaminase rise. For example, manage dosing for second level of transaminase rise (i.e., AST or ALT >5.0×ULN and ≤8.0×ULN, if normal at baseline, or AST or ALT >2.0×baseline and ≤12.5×ULN, if elevated >ULN at baseline) as instructed for the third level of transaminase rise (i.e., AST or ALT >8.0×ULN and ≤20.0×ULN, if normal at baseline, or AST or ALT >12.5×ULN and ≤20.0×ULN, if elevated >ULN at baseline)
 
For the third and fourth levels of transaminase rises, permanently discontinue study drug/study regimen
		

Nephritis or renal dysfunction (elevated serum
	
Any Grade
	
General Guidance
	
For Any Grade:
 
 
Consult with nephrologist.
 
Monitor for signs and symptoms that may be related to changes in renal function (e.g., routine urinalysis, elevated serum BUN and
 

creatinine)			
creatinine, decreased creatinine clearance, electrolyte imbalance, decrease in urine output, or proteinuria, recent IV contrast, medications, fluid status).
 
 
- Patients should be thoroughly evaluated to rule out any alternative etiology (e.g., disease progression or infections).
 
- Steroids should be considered in the absence of clear alternative etiology even for low-grade events (Grade 2), in order to prevent potential progression to higher grade event.
 

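### Appendix F and section 3.4.2.4 do not give HCC patients one dosing instruction for an isolated bilirubin rise, or for a grade 2 AST/ALT rise

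*Combined protocol and SAP*

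**What the plan says.** Appendix F (section 16.6) has general hepatitis rows that grade AST, ALT and total bilirubin, with bilirubin able to set the grade on its own. With a normal baseline, bilirubin is grade 2 above 1.5 and up to 3 × ULN, grade 3 above 3 and up to 10 × ULN, and grade 4 beyond that. Transaminases above 8 × ULN "or elevations in bilirubin" above 5 × ULN lead to permanent discontinuation.

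Beside these rows stands a redirection for HCC patients: "PLEASE SEE shaded area immediately below this section to find guidance for management of" elevated LFTs in HCC. The shaded area it points to is marked as being for HCC patients alone. Its first row is headed "Any Elevations of AST, ALT, or TB as Described Below" and carries monitoring and work-up. Four dosing levels follow, each defined by an isolated AST or ALT range. The last row begins "If transaminase rise is not isolated but (at any time) occurs in setting of either increasing total/direct bilirubin" and moves the patient to the next transaminase level.

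Section 3.4.2.4 gives three caveats on how HCC patients are to be read against Appendix F, all in grades and covering transaminases and/or bilirubin:

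- With a normal baseline, a grade 2 event means a hold.
- With a baseline already raised to grade 1 or 2, a later grade 2 elevation does not mean a hold.
- "Grade 3 events will be treated as per" Appendix F, whatever the baseline.

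**The concern.** Section 3.4.2.4 hands HCC patients to Appendix F by grade, for bilirubin as well as transaminases. The part of Appendix F written for those patients contains no grades and no dosing level that bilirubin alone can trigger. For an isolated bilirubin rise, the cross-reference therefore leads to no specific HCC instruction. For AST/ALT it leads to an instruction that disagrees with section 3.4.2.4.

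The situation is foreseeable. Section 3.4.2.4 itself describes raised and fluctuating transaminases and/or bilirubin as common in HCC. The eligibility rules also admit patients with cirrhosis whose only scored abnormality is bilirubin, as shown in the working.

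Whether a patient is held, stopped or continued affects that patient's safety and exposure. It also bears on feasibility, part of the secondary objective. Section 10 opens the ablation arms after the first 10 patients of cohorts A1 and B, probably if 7 or more of 10 complete treatment, and all of A1 has HCC. If exactly seven A1 patients completed under one reading, a different reading for one of them would give 7 − 1 = 6.

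**Working it through.** **1. Who is covered.** The Précis lists "cohorts A1 (HCC; Barcelona clinic liver cancer staging system (BCLC) stage C; N=10), A2 (HCC; BCLC stages B/C; N=30) and B (BTC; N=30". The total is 10 + 30 + 30 = 70. This matches section 10, "As each of these 7 treatment arms of 10 patients will be considered a small pilot": 7 × 10 = 70. HCC patients number 10 + 30 = 40, and 40/70 = 57.1%. These are planned evaluable patients. Section 10 also states "The accrual ceiling for the protocol will be set at 90 patients", without giving the HCC share of that ceiling.

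**2. What triggers a dosing instruction in the HCC area.**

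- Level 1: isolated AST/ALT above ULN and up to 5 × ULN, whatever the baseline. No dose modification.
- Level 2: above 5 and up to 8 × ULN (normal baseline), or above 2 × baseline and up to 12.5 × ULN (raised baseline). Hold.
- Level 3: above 8 and up to 20 × ULN (normal baseline), or above 12.5 and up to 20 × ULN (raised baseline). Hold, with a 14-day limit.
- Level 4: above 20 × ULN. Permanent discontinuation.
- Bilirubin: escalates an accompanying transaminase rise, or contributes to Hy's law at level 3.

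Hy's law, as defined in the general rows, needs AST and/or ALT above 3 × ULN together with bilirubin above 2 × ULN. The reportable hepatic abnormality in sections 3.4.2.4 and 8.5.2.2, with its dosing interruption, needs the same pair. With normal AST/ALT neither is met, so neither closes the gap.

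**3. Isolated bilirubin, AST/ALT normal, normal baseline.** Grades are those printed in Appendix F.

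| Bilirubin | General hepatitis rows | HCC area | Section 3.4.2.4 | Other Immune Mediated Reactions | Non-Immune-Mediated Reactions |
|---|---|---|---|---|---|
| 2 × ULN (grade 2) | only the Hy's law line is legible | no dosing line | hold | hold | hold |
| 4 × ULN (grade 3) | hold; stop if not grade 1 or lower within 14 days | no dosing line | per Appendix F | hold | hold, with 7- and 14-day limits |
| 6 × ULN (grade 3) | permanent discontinuation | no dosing line | per Appendix F | hold | hold, with 7- and 14-day limits |
| 11 × ULN (grade 4) | permanent discontinuation | no dosing line | per Appendix F | discontinue | discontinue, subject to judgement for laboratory values |

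The General Considerations table adds a hold at grade 2, a pointer to the specific guidelines at grade 3, and discontinuation at grade 4. The sharpest divergence is at 6 × ULN: stop, hold, or no HCC dosing line. No sentence ranks these sources for an HCC patient.

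**4. Grade 2 AST/ALT, normal baseline.** Appendix F defines grade 2 as above 3 and up to 5 × ULN. HCC level 1 runs from above ULN up to 5 × ULN, so it contains the whole grade 2 range. Section 3.4.2.4 holds treatment there. HCC level 1 makes no dose change unless the investigator judges the worsening significant. This conflict does not depend on bilirubin.

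**5. Foreseeability.** With cirrhosis, bilirubin is limited only through Child-Pugh A/B7 (sections 2.1.1.6 and 2.1.1.8). In Appendix B, bilirubin above 3 mg/dL scores 3 and each of the other four items scores at least 1. The total 3 + 1 + 1 + 1 + 1 = 7 still meets that criterion.

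**The case against.** The strongest reply is that a workable reading exists. Section 3.4.2.4 speaks in grades, and only the general hepatitis rows carry grades, so it may intend HCC patients to be read against those rows. The redirection does not expressly switch the general rows off. This reading is possible, but it is not stated. It strains against a redirection that sends HCC patients elsewhere, and it leaves the AST/ALT conflict in place.

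Several other points stand and limit the conclusion.

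- A reader might infer that a grade 3 bilirubin rise in an HCC patient calls for no action. The documents do not support that. The HCC heading row requires monitoring and evaluation of other causes, and the generic rows give a grade 3 hold. What is missing is a statement of which dosing instruction governs.
- A reader might infer that sites will diverge. The protocol describes treatment at one clinical centre, weekly team review of each patient, and review of adverse events by the principal investigator. The ambiguity is in the text; divergence between sites is not shown.
- A reader might infer that 6 × ULN always ends treatment for a biliary patient. It does so only if the event is managed as immune-mediated, after other causes have been considered.
- Section 10 tabulates adverse events by grade, and that table does not use the dosing row. The effect on the A1 gate is a possibility, not a forecast.

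The table has also suffered in extraction. The general grade 2 dosing cell shows only the Hy's law line, so nothing here rests on it. All four transaminase levels are present and the escalation row refers to them consistently. A missing bilirubin row therefore seems unlikely, although that row would not have counted one.

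**Conclusion.** The point holds as a conflict between stated safety rules. In the HCC area, bilirubin has no dosing level of its own, while section 3.4.2.4 presumes graded bilirubin rules for these patients. At 6 × ULN with normal AST/ALT, the documents can be read as permanent discontinuation, as a hold, or as giving no HCC dosing line. Section 3.4.2.4 and HCC level 1 also contradict each other over the whole grade 2 AST/ALT range at normal baseline.

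The instruction covers 40 of 70 planned patients. A reader might take that as the number affected, but the documents give no rate of isolated bilirubin rises, so the number who would meet the gap is unknown. The bilirubin example assumes AST/ALT within normal limits, a normal baseline and management as immune-mediated. It also assumes that no bilirubin row was lost from the shaded area. The AST/ALT conflict needs only a normal baseline. No view is taken on which rule is clinically right.

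**What to change.** Reconcile section 3.4.2.4, the general and HCC hepatitis rows of Appendix F, and its generic immune-mediated and non-immune-mediated rows. For an HCC patient, each level of isolated bilirubin elevation and a grade 2 AST/ALT elevation should each have one stated dosing instruction, by baseline status where that matters. The text should also say which source governs if more than one could apply. The content is for the clinical team.

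The cost is a few lines in an amendment. No tests are added: total and direct bilirubin are in the biochemical profile, which the study calendar already schedules weekly through cycles 1 to 4.

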2.1.1.7 Age  $\geq 18$  years

2.1.1.8 Patients must have normal organ and marrow function as defined below:

leukocytes	$\geq 3,000/\text{mcL}$
absolute neutrophil count	$\geq 1,000/\text{mcL}$
platelets	$\geq 60,000/\text{mcL}$
total bilirubin	If cirrhosis present: Part of Child Pugh requirement If no cirrhosis: bilirubin should be $\leq 2 \times$ ULN
serum albumin	If cirrhosis present: Part of Child Pugh requirement If no cirrhosis: albumin should be $\geq 2.5\text{g/dl}$
Patients are eligible with ALT or AST up to $5 \times$ ULN.	
creatinine	$< 1.5 \times$ institution upper limit of normal OR
creatinine clearance	$\geq 45 \text{ mL/min/1.73 m}^2$ for patients with creatinine levels above institutional normal

2.1.1.9 Patients must have recovered from any acute toxicity related to prior therapy, including surgery. Toxicity should be  $\leq$  grade 1 or returned to baseline.

2.1.1.10 Patients must not have other invasive malignancies within the past 5 years (with the exception of non-melanoma skin cancers, non-invasive bladder cancer or localized prostate cancer for whom systemic therapy is not required).

2.1.1.11 Patient must be able to understand and willing to sign a written informed consent document.

2.1.1.12 Evidence of post-menopausal status or negative urinary or serum pregnancy test for female pre-menopausal patients. Women will be considered post-menopausal if they have been amenorrheic for 12 months without an alternative medical cause. The following age-specific requirements apply:

- Women  $< 50$  years of age would be considered post-menopausal if they have been amenorrheic for 12 months or more following cessation of exogenous hormonal treatments and if they have luteinizing hormone and follicle-stimulating hormone levels in the post-menopausal range for the institution or underwent surgical sterilization (bilateral oophorectomy or hysterectomy).
- Women  $\geq 50$  years of age would be considered post-menopausal if they have been amenorrheic for 12 months or more following cessation of all exogenous hormonal treatments, had radiation-induced menopause with last menses  $> 1$  year ago, had chemotherapy-induced menopause with last menses  $> 1$  year ago, or underwent surgical

sterilization (bilateral oophorectomy, bilateral salpingectomy or hysterectomy). Subject is willing and able to comply with the protocol for the duration of the study including undergoing treatment and scheduled visits and examinations including follow up.

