
Isolated AST or ALT >5.0×ULN and <math>\leq 8.0 \times \text{ULN}</math>, if normal at baseline
 
Isolated AST or ALT >2.0×baseline and <math>\leq 12.5 \times \text{ULN}</math>, if elevated >ULN at baseline
	
 
Hold study drug/study regimen dose until resolution to AST or ALT <math>\leq 5.0 \times \text{ULN}</math>.
 
If toxicity worsens, then treat as described for elevations in the rows below.
 
If toxicity improves to AST or ALT <math>\leq 5.0 \times \text{ULN}</math>, resume study drug/study regimen after completion of steroid taper
 
	
 
Regular and frequent checking of LFTs (e.g., every 1 to 3 days) until elevations of these are improving or resolved.
 
Recommend consult hepatologist; consider abdominal ultrasound, including Doppler assessment of liver perfusion.
 
Consider, as necessary, discussing with study physician.
 
If event is persistent (>2 to 3 days) or worsens, and investigator suspects toxicity to be immune-mediated AE, recommend to start prednisone 1 to 2 mg/kg/day PO or IV equivalent.
 
If still no improvement within 2 to 3 days despite 1 to 2 mg/kg/day of prednisone PO or IV equivalent, consider additional workup and treatment with IV methylprednisolone 2 to 4 mg/kg/day.
 
If still no improvement within 2 to 3 days despite 1 to 2 mg/kg/day of IV methylprednisolone, consider additional abdominal workup (including liver biopsy) and imaging (i.e., liver ultrasound), and consider starting immunosuppressives (i.e., mycophenolate mofetil 0.5 – 1 g every 12 hours then taper in consultation with hepatology consult). Discuss with study physician if mycophenolate mofetil is not available. Infliximab should NOT be used.
 
	
Regular and frequent checking of LFTs (e.g., every 1-2 days) until

Isolated AST or ALT
	
 
Hold study drug/study regimen dose
 
	
Regular and frequent checking of LFTs (e.g., every 1-2 days) until
	

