	
>8.0×ULN and ≤20.0×ULN, if normal at baseline
 
Isolated AST or ALT >12.5×ULN and ≤20.0×ULN, if elevated >ULN at baseline
	
until resolution to AST or ALT ≤5.0×ULN
 
 
Resume study drug/study regimen if elevations downgrade to AST or ALT ≤5.0×ULN within 14 days and after completion of steroid taper.
 
Permanently discontinue study drug/study regimen if the elevations do not downgrade to AST or ALT ≤5.0×ULN within 14 days
 
Permanently discontinue study drug/study regimen for any case meeting Hy’s law criteria, in the absence of any alternative cause.
 
	
elevations of these are improving or resolved.
 
 
Consult hepatologist (unless investigator is hepatologist); obtain abdominal ultrasound, including Doppler assessment of liver perfusion; and consider liver biopsy.
 
Consider, as necessary, discussing with study physician.
 
If investigator suspects toxicity to be immune-mediated, promptly initiate empiric IV methylprednisolone at 1 to 4 mg/kg/day or equivalent.
 
If no improvement within 3 to 5 days despite 1 to 4 mg/kg/day methylprednisolone IV or equivalent, obtain liver biopsy (if it has not been done already) and promptly start treatment with immunosuppressive therapy (mycophenolate mofetil). Discuss with study physician if mycophenolate is not available. Infliximab should NOT be used.
 
Once the patient is improving, gradually taper steroids over ≥28 days and consider prophylactic antibiotics, antifungals, and anti-PCP treatment (refer to current NCCN guidelines for treatment of cancer-related infections)
 

	
Isolated AST or ALT >20×ULN, whether normal or elevated at baseline
	
Permanently discontinue study drug/study regimen
	
Same as above (except would recommend obtaining liver biopsy early)

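### Appendix F, HCC hepatitis rows: with baseline ALT/AST above 2.5 × ULN, on-treatment values above 5 × ULN and up to twice baseline fall in no dosing row (minor safety correction)

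*Combined protocol and SAP*

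**What the plan says.** Section 2.1.1.8: "Patients are eligible with ALT or AST up to" 5 × ULN. Appendix F (16.6) has general hepatitis rows and a shaded block for HCC. The general rows direct HCC patients to that block, which is labelled as being for them only. Within it, for isolated AST or ALT:

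- **Level 1, no dose change:** above ULN and up to 5.0 × ULN, "whether normal or elevated at baseline". It is handled as level 2 if the rise "represents significant worsening based on investigator assessment".
- **Level 2, hold:** with a normal baseline, above 5.0 and up to 8.0 × ULN; with a raised baseline, above "2.0×baseline and ≤12.5×ULN, if elevated" at baseline. The instruction is "Hold study drug/study regimen dose until resolution to AST or ALT" ≤5.0 × ULN.
- **Level 3, hold, with permanent discontinuation if not back to ≤5.0 × ULN in 14 days:** with a normal baseline, above 8.0 and up to 20.0 × ULN; with a raised baseline, above "12.5×ULN and ≤20.0×ULN, if elevated" at baseline.
- **Level 4, permanent discontinuation:** above 20 × ULN.

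A separate rule covers a rise that is not isolated. The triggers are increasing bilirubin (at least 1.5 × ULN if normal at baseline, or twice baseline if raised) or signs of liver decompensation such as fever or raised INR. It reads: "Manage dosing for each level of transaminase rise as instructed for the next highest level of transaminase rise". It restates level 2 with the same limits.

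Section 3.4.2.4 adds caveats for HCC. Under caveat 2, for patients with raised transaminases and/or "bilirubin at baseline (grade 1 or 2 i.e. still allowing for study entry"), a later Grade 2 rise does not lead to a hold. Caveat 3 sends Grade 3 events to Appendix F whatever the baseline.

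**The concern.** For a raised baseline, level 1 ends at a multiple of ULN while level 2 starts at a multiple of the patient's own baseline. The two limits coincide only when baseline is 2.5 × ULN. Above that there is a gap; below it there is an overlap.

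What is at stake is consistent dosing after a possible immune-mediated hepatitis. Two investigators could both work from the table, and one continue while the other holds. The non-isolated case is worse. The step-up rule is meant to be stricter when bilirubin is rising or decompensation appears, and it cannot be applied to a value that has no level. The situation is plausible: section 3.4.2.4 says that raised and fluctuating liver tests are common in HCC, and the calendar in section 3.6 has biochemistry drawn weekly in cycles 1 to 4.

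**Working it through.** Let b be baseline and y the on-treatment value, both in × ULN. Eligibility gives b ≤ 5. There is no stated figure in the plan to reproduce, so the check is whether the rows cover every y above 1 exactly once.

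**Raised baseline (b > 1), as written**

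- Level 1: 1 < y ≤ 5
- Level 2: 2b < y ≤ 12.5
- Level 3: 12.5 < y ≤ 20
- Level 4: y > 20

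No row applies when y > 5 and y ≤ 2b. This needs 2b > 5, so b > 2.5. Two rows apply when 2b < y ≤ 5. This needs 2b < 5, so b < 2.5.

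| b | No row for y | y/b at the lower edge (5/b) |
|---|---|---|
| 2.5 | none | – |
| 3 | above 5 to 6 | 1.67 |
| 4 | above 5 to 8 | 1.25 |
| 4.8 | above 5 to 9.6 | 1.04 |
| 5 | above 5 to 10 | 1.00 |

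An overlap example is b = 2, y = 5: level 1 applies because y ≤ 5, and level 2 applies because y > 4.

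A grid check (b to 5.00 in steps of 0.01, y from 1.05 to 25.0 in steps of 0.05) found uncovered points exactly where 2.5 < b ≤ 5 and 5 < y ≤ 2b. Overlaps occurred only for raised baselines below 2.5.

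**Normal baseline, as written.** The ranges 1–5, 5–8, 8–20 and above 20 cover every value once, so there is no gap.

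**Non-isolated rise: b = 4, bilirubin 1.8 × ULN, normal at baseline**

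- ALT 4.9: level 1, handled as level 2, a hold row whose release limit is already met.
- ALT 7: no level, so no step up is possible.
- ALT 8.1: level 2 (8.1 > 8), handled as level 3.

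ALT 7 therefore receives less instruction than ALT 4.9.

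**Grade of the uncovered values.** With an abnormal baseline, the general hepatitis rows print Grade 1 as 1.5–3.0 × baseline, Grade 2 as above 3 to 5, and Grade 3 as above 5 to 20. An uncovered value has y/b above 1 and at most 2, so it is ungraded or Grade 1; 7/4 = 1.75 is Grade 1. On a ULN scale the same rows end Grade 2 at 5.0 × ULN (the limits for a normal baseline), so every uncovered value would be Grade 3.

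**The case against.** The strongest reply is that the documents already answer the question. Appendix F's General Considerations grade dose modifications by CTCAE v5.0 and require none at Grade 1. The printed grading is relative to baseline when baseline is abnormal, so uncovered values are at most Grade 1. Caveat 2 does not hold drug even at Grade 2. HCC patients are sent away from the general hepatitis rows, but not from the General Considerations. On this reading the answer is to continue.

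That reading is legitimate. A reader might infer that these values must lead to a hold, or that the choice rests on investigator judgement alone. The documents support neither.

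The reading does not settle the matter, though:

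- Level 1 is the only no-change row. It expressly includes raised baselines and stops at 5.0 × ULN.
- Levels 2 and 3 release only at ≤5.0 × ULN.
- Caveat 2 ties a baseline of Grade 1 or 2 to study entry. That fits a ULN scale, because the entry limit and the normal-baseline Grade 2 limit are both 5 × ULN. On that scale caveat 3 sends the value to Appendix F, where no HCC row matches.
- Sections 6.5 and 8.1.4 name CTCAE v4.0, while Appendix F names v5.0.
- Neither reading supplies a starting level for the step-up rule.

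Other safeguards reduce the risk without assigning a row. Section 8.5.2.2 interrupts dosing when bilirubin also exceeds 2 × ULN and no unrelated diagnosis is established. Section 7.4.1 provides weekly team discussion and review by the principal investigator. The level 1 clause on significant worsening does not help, because it belongs to a row that ends at 5.0 × ULN.

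**Conclusion.** The gap and the overlap are certain on the text: no row for 2.5 < b ≤ 5 with 5 < y ≤ 2b, and two rows for a raised b below 2.5 with 2b < y ≤ 5. It is a minor patient-safety correction to a stated dosing rule. The documents point to continuing under baseline-adjusted grading and to holding under ULN-based grading. The clearest defect is that the step-up rule fails for non-isolated rises.

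The number affected is unknown, because no baseline ALT/AST distribution is given. As an assumption only, if 5%, 10% or 20% of the 40 planned HCC patients (10 in A1, 30 in A2) had a baseline above 2.5 × ULN, 2, 4 or 8 would be exposed. If all 20 places between the 70 evaluable and the ceiling of 90 went to HCC, the same shares of 60 give 3, 6 or 12. Only patients whose later value lands in the gap would be affected.

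A reader might also infer that the efficacy evaluation is compromised. Nothing in the documents supports that: the exact binomial assessment of 6-month PFS does not use these limits.

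**What to change.** Assign the uncovered values to a row, both in level 2 itself and where the step-up rule restates it.

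**Conservative version.** Set level 2 for a raised baseline to above 5.0 and up to 12.5 × ULN. The levels become 1–5, 5–12.5, 12.5–20 and above 20, so each value falls in one row and the overlap also goes. Every eligible baseline can reach the ≤5.0 × ULN release limit. This agrees with caveat 2 only if the caveats use ULN-based grading. Its downsides are:

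- Small rises at a high baseline lead to a hold. For example, 4.8 to 5.2 × ULN is 5.2/4.8 = 1.08, an 8% rise.
- A non-isolated value in the former gap is handled as level 3, so failure to return to ≤5.0 × ULN within 14 days means permanent discontinuation.
- Low-baseline values up to 5 × ULN (such as 1.2 rising to 4.8) lose their nominal level 2 match and are held only through the significant-worsening clause. Little is lost, since the level 2 release limit is already met there.

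**Alternative, if the clinical team and manufacturer prefer a relative limit.** Extend level 1 to ≤5.0 × ULN, or ≤2.0 × baseline if raised at baseline. Isolated gap values then continue, and non-isolated ones are at least held under level 2. This alone leaves the overlap below b = 2.5. Starting level 2 above the larger of 5.0 × ULN and 2.0 × baseline removes it; since 2b ≤ 10 < 12.5, the rows then fit together.

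Under either version, state in section 3.4.2.4 which grading scale the caveats use. The cost is a short protocol amendment with IRB approval, manufacturer confirmation because a dated guideline is being edited, and a note to the study team.
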